- Rub area to be cleansed with a back and forth motion
- Use 1 cloth for neck, arms, and legs (stopping at ankles to prevent wiping of feet/heels)
- Use second cloth for torso and back

CHG Bath Intervention. Subjects whose parents consent for this study will receive a CHG bath twice weekly. The CHG baths will be performed by 1 of 5 trained study nurses on each unit to ensure a standard bathing technique. Baths will be performed every Monday and Thursday during the day shift, for up to 12 weeks post enrollment or until the CVC is removed or the patient is discharged. Nurses will use pre-warmed 2% CHG impregnated non-sterile cloths from Sage Products Inc. CHG bath cloths will be pre-warmed to 100°F (37.8°C) in the warmers provided by Sage Products Inc. Baths will entail cleaning the infants with 2 CHG bathing cloths (1 package) beginning at the neck, working down the body toward the feet. Nurses will be instructed not to use the CHG cloths on the face, scalp, or over open body orifices or wounds, including the genitalia and anus (where bloodstream absorption is enhanced). The genital and anal areas will be protected by placing a clean diaper on the study subject prior to initiation of CHG bath. Cleansing of the feet/heels with CHG will be avoided due to the possibility of blood sample contamination as explained by Cowen et al (1979). Nurses will document completion of the CHG baths on the CHG Bath Data Collection Tool that will be kept at each participant's bedside. When a bath needs to be delayed for clinical reasons, it will be done as close to the scheduled time as possible.

Cleansing between CHG baths: Cleansing of infants between CHG baths may be required if they become soiled. These baths or partial baths will be done per NICU standard of care using (non-CHG) Comfort Cloths by Sage Products Inc. and documented on the CHG Exposure and Comfort Cloth Bath Log (Appendix C).

CHG Exposure: Infant participants have the potential for additional CHG exposures for central line insertions, dressing changes, and perioperative bathing. Additional CHG exposures will be recorded on the CHG Exposure and Comfort Cloth Bath Log.

Monitoring for Adverse Events

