Phototherapy. To track study participants who are receiving phototherapy we will include a data collection point on the CHG Skin Assessment Log. This data collection point will enable the RN completing every 12 hours skin assessments to indicate if the infant is receiving phototherapy. This will allow the investigators to determine if a relationship between CHG level and phototherapy exists.

Study Participation Ends. Infants will remain in the study up to 48 weeks PMA (maximum of 12 weeks), upon hospital discharge/transfer, or until the CVC is removed.

Data Management and Quality Control. The Cardiovascular and Critical Care Nursing Research Group (CCNRRG) will be responsible for all data management procedures and will provide support to the research team during the course of the investigation. The CCNRRG employs experienced research personnel. Also all study staff will be CITI program trained. Study staff will have access to designated desk spaces and hospital maintained computer and printing systems.

Standard procedures to ensure accurate and reliable collection of data will include well designed forms with clear instructions, training of staff, and on-going monitoring of all study activities. A manual of operations that describes the purpose of the study, eligibility criteria, and all intervention and assessment procedures will be developed by the study investigators. Study staff will be trained by the study investigators to conduct informed consent, bathing technique, research assessments, and complete case report forms. Furthermore, the primary investigator will provide oversight of all research activities to ensure proper data collection procedures and to monitor staff performance.

Subject confidentiality will be maintained using unique study identification codes. The CHG Active Study Participant Log (Appendix J) will be used to assign ID numbers and to record the identifiers for contacting and tracking subjects. An electronic copy of the log will be kept by the data manager in a file accessible only to study staff, in a computer folder with restricted access. Identifiable data, such as patient name, contact information and medical record numbers will be recorded and stored separately from the research data.

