Random observations of CHG baths will be performed throughout the entire study period by a designated clinician to ensure that all nurses are bathing the infants using the same technique. Each study team member actively bathing study subjects will be audited a minimum of once every two months. These observations will be documented on the CHG Bath Audit Tool (Appendix K) and scores of 15/15 points are acceptable. Any score lower than 15 will require retraining on the bathing technique. Also to facilitate reliable assessment of skin lesions, a CHG Erythema Assessment Tool (Appendix L) will be available for nurses to follow during their assessments (maintained at each study patients' bedside) (Figure 1.).

The sponsor-investigator will also engage the services of a qualified independent monitor to ensure the protection of the rights of human subjects, the safety of all subjects involved in the investigation and the quality and integrity of the data resulting from the trial. The independent monitor will conduct a pre-monitoring set-up visit and a monitoring visit after every fifth patient has been recruited and on the study for 1 week.

Data Analysis. With the support of a faculty statistician from the BCH Center for Patient Safety and Quality Research, we will use descriptive statistics including mean, median, range, and frequencies to describe the study sample and the findings (skin findings and adverse events). We will characterize the study sample on demographic and clinical characteristics. Our primary outcome measures will be proportion of subjects that experience any adverse event, and the rate of adverse events per 100 patient-days of follow-up. Our inferential statistics will calculate 95% confidence intervals around these estimates.

Research Question 1:

Are twice weekly CHG baths safe for use in a sample of infants 36 weeks PMA or older, and less than 2 months of age (48 weeks PMA) with a CVC?

Data Analysis 1:

Descriptive statistics including mean, median, range and frequencies will be used to describe adverse events (including skin reactions and other untoward events). We will characterize the demographic and clinical characteristics of subjects that experience adverse events, although we will not perform hypothesis tests of association. We will consider time-to-rash data using Kaplan-Meier estimators.

Research Question 2:

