Does twice weekly CHG baths lead to rising (cumulative) CHG blood levels, liver function tests (LFTs -AST/ALT) and Serum Creatinine over time in a sample of infants 36 weeks PMA or older, and less than 2 months of age (48 weeks PMA) with a CVC?

Data Analysis 2:

Descriptive statistics including mean, median, range and frequencies will be used to describe CHG, LFTs and serum Creatinine blood levels over time. We will examine scatterplots and other graphical analysis of blood level dispersion over time to look for relationships.

Sample Size Justification. The primary quantitative goal of this study is estimation of the adverse event rate per 100 patient days. The study sample size will impact the precision of this estimate, and we will establish an upper bound on the rate if zero adverse events occur. In this context, we designed the study sample to expand the existing knowledge base.

Based on recent safety data (Quach, et al 2014) on roughly 200 neonates which recorded no adverse events, we assume the rate of adverse events using CHG bath is lower than 5 events per 1000 days of post-exposure follow-up. We propose following N=50 subjects over 7 days of post-exposure follow-up, for a total of 350 observation days. Assuming rates of 3.5 events or 1.0 events per 1000 days of follow-up, the probability that at least one subject will experience an adverse event is roughly 83% or 40% respectively. Using Monte Carlo simulations, the mean upper bound for estimable rates is 5.5 events per 1000 days.

Auditing and Inspecting:

The sponsor-investigator will permit study-related monitoring, audits, and inspections by the Boston Children's Hospital IRB, the independent data monitor and government regulatory bodies, of all study related documents (e.g. source documents, regulatory documents, data collection instruments, study data etc.). The Investigator will ensure the capability for inspections of applicable study-related facilities.

Human Subjects:

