Holding rules for patients that become clinically unstable. For the safety of the study participant bathing will be suspended for infants demonstrating significant or acute impairment of their clinical status as indicated by their medical team. For example, patients requiring volume resuscitation due to blood and fluid losses, or a patient in the immediate post-operative period will not be bathed until return to baseline stability. These patients will have 2 CHG levels obtained within 1 week of last CHG bath, unless previous level was non-detectable. Infants deemed not appropriate for participation by either the study team or medical team will have monitoring of daily vital signs (ranges-heart rate, respiratory rate, blood pressure, oxygenation requirement and means of respiratory support) for 1 month from cessation of CHG baths or until discharge, whichever comes first.

Stopping rules for subjects that become clinically unstable. Study subjects whose clinical status does not return to baseline, as assessed by both the study and medical teams will be removed from the study after completing the clinical monitoring for 1 month as described above.

Table 1: Management of Adverse Events to CHG Baths

Erythema Assessment (see CHG Erythema Assessment Tool for visual comparisons)			
Finding	Action	Follow Holding and Stopping Rules	Reporting
1. Mild redness X1	None	Not Applicable	No immediate action; Send email update to PI; include in monthly DSMP report
2. Mild redness X2, persistent redness leading up to 2 nd bath, or moderate redness:	Discontinue CHG baths (unless rash is limited only to diaper area)	Adverse Event (Other Than Anemia)	Immediately reportable to PI; include in monthly DSMP report
3. Raised rash	Discontinue CHG baths (unless rash is limited only to diaper area)	Adverse Event (Other Than Anemia)	Immediately reportable to PI; include in monthly DSMP report
4. Blister(s)	Discontinue CHG baths	Adverse Event (Other Than Anemia)	Immediately reportable to PI; meet with DSMC
5. Open area(s)	Discontinue CHG baths	Adverse Event (Other Than Anemia)	Immediately reportable to PI; meet with DSMC

6. Evidence of systemic event	Discontinue CHG baths	Adverse Event (Other Than Anemia)	Immediately reportable to PI; meet with DSMC
7. Anaphylaxis	Discontinue CHG baths	Adverse Event (Other Than Anemia)	Immediately reportable to PI; meet with DSMC
Lab Value Assessment			

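### The adverse event rate is sized on 7 days per infant but reported over up to 12 weeks, so the stated precision is not that of the reported rate and one pooled figure can hide a change in risk

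*Combined protocol and SAP*

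**What the plan says.** The Sample Size Justification names the adverse event rate per patient-day as the main quantitative goal. On the basis of an earlier neonatal cohort, "we assume the rate of adverse events using CHG bath is lower than 5 events per 1000 days of post-exposure follow-up". The person-time is then set: "We propose following N=50 subjects over 7 days of post-exposure follow-up, for a total of 350 observation days". From this the section derives its operating figures. "Assuming rates of 3.5 events or 1.0 events per 1000 days of follow-up", it says, "the probability that at least one subject will experience an adverse event is roughly 83% or 40% respectively". It adds a simulated mean upper bound of 5.5 per 1000 days.

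Follow-up elsewhere is much longer. Under CHG Bath Intervention, baths continue "for up to 12 weeks post enrollment or until the CVC is removed or the patient is discharged". Under Study Participation Ends, "Infants will remain in the study up to 48 weeks PMA (maximum of 12 weeks"), with earlier exit at discharge, transfer or catheter removal.

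The Data Analysis section gives two primary measures: the proportion of infants with any adverse event, and "the rate of adverse events per 100 patient-days of follow-up". Both get 95% confidence intervals. The rate has no window and no split by time since the first bath.

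In Table 1, a single mild redness needs no action. From the second row on ("Mild redness X2, persistent redness leading up to 2 nd bath, or moderate redness"), the listed action is to discontinue baths, apart from findings limited to the diaper area in rows 2 and 3.

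**The concern.** Two things follow from setting these sections side by side.

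First, the quantity sized (a rate over 7 days per infant) differs from the quantity defined for analysis (a rate over all follow-up). The probabilities and the bound in the sample size section therefore do not describe the interval that will be published.

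Second, a single events-per-day figure summarises risk well only if the daily risk is roughly constant. The design gives reason to doubt that. Infants who react mostly stop being bathed, so bathed days after the first week are contributed mainly by infants who tolerated the first baths. That selection would pull the rate down over time. Research Question 2, on the other hand, asks whether chlorhexidine, liver enzymes and creatinine rise with repeated baths, which would push the rate up. One pooled number shows neither pattern. In a safety pilot meant to support a larger study, a reader could take it as the risk of the first baths, or of prolonged bathing, when it is a mixture weighted by length of stay.

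**Working it through.** **Inputs.** From the Sample Size Justification: 50 infants, 7 days each, rates of 3.5 and 1.0 per 1000 days, stated results 83%, 40% and 5.5 per 1000. From CHG Bath Intervention: a cap of 12 weeks (84 days). From Setting: mean stays of 12.7 days (NICU) and 9-15 days (cardiac unit, under 2 months). The plan gives no expected time on study, so using stays as time after the first bath is an assumption.

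**1. The plan's own figures.** With T = 50 × 7 = 350 days, P(at least one event) = 1 − exp(−rate × T).
- At 3.5 per 1000: 1 − exp(−1.225) = 70.6% (stated: 83%).
- At 1.0 per 1000: 1 − exp(−0.350) = 29.5% (stated: 40%).
- Solving backwards: −ln(0.17)/0.0035 = 506 days and −ln(0.60)/0.001 = 511 days. Both stated values fit about 506-511 days, not 350.
- Zero-event upper bound at 350 days: −ln(0.05)/350 = 8.6 per 1000 (one-sided 95%), or −ln(0.025)/350 = 10.5 per 1000 (two-sided 95%). Zero events gives the smallest exact limit, so no average of exact 95% upper limits at 350 days can be as low as 5.5. A one-sided zero-event bound of 5.5 would need −ln(0.05)/0.0055 = 545 days. The simulation is not described, so 5.5 cannot be traced further.

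**2. Person-time under the actual follow-up rules.** Assume exponential follow-up with mean m, capped at 84 days. Expected days per infant are m(1 − exp(−7/m)) in week one and m(1 − exp(−84/m)) in total. For 50 infants:

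| m (days) | Week-one days | Total days | Share after day 7 |
|---|---|---|---|
| 9 | 243 | 450 | 46% |
| 12.7 | 269 | 634 | 58% |
| 15 | 280 | 747 | 63% |

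So 350 matches neither column: some infants leave before day 7 and others stay well beyond it. The two-sided zero-event bound moves accordingly: 3.689/269 = 13.7 per 1000 on week one, and 3.689/634 = 5.8 on all days, at m = 12.7.

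**3. Pooled against early rate.** Let f be the later rate divided by the week-one rate. With the same follow-up of D days for every infant, pooled/early = [7 + (D − 7)f]/D.

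| f | D = 9 | D = 12.7 | D = 15 |
|---|---|---|---|
| 0 (all events in week one) | 0.78 | 0.55 | 0.47 |
| 0.25 | 0.83 | 0.66 | 0.60 |
| 0.5 | 0.89 | 0.78 | 0.73 |
| 1 (constant) | 1.00 | 1.00 | 1.00 |
| 2 (rising) | 1.22 | 1.45 | 1.53 |

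With exponential follow-up and f = 0, the ratio is week-one days over total days: 243/450 = 0.54, 269/634 = 0.42, 280/747 = 0.37.

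**4. The selection mechanism alone.** Suppose a fraction s of infants is susceptible with daily hazard h, the rest have no risk, and an infant leaves at the event. Events by day t are s(1 − exp(−ht)) and person-time is (1 − s)t + s(1 − exp(−ht))/h. For s = 0.1 and h = 0.1, the rate is 7.40 per 1000 over 7 days and 5.92 over 12.7 days, a ratio of 0.80. Over the cases tried (s of 0.1-0.2, h of 0.05-0.2), the ratio was 0.60-0.90 at 12.7-15 days. These s and h are illustrative and not from the documents.

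**The case against.** The strongest reply is that the direction of any distortion is unknown. A reader might infer from the follow-up rules that the pooled rate will roughly halve the early risk. The documents do not support that. Halving needs almost no events after day 7 with mean follow-up near 14 days, and nothing in the protocol says reactions cluster at the first baths. Several Table 1 findings need repetition or can arise at any time: repeated or persistent redness, raised liver enzymes or creatinine, and anaemia. Selection by itself gave milder ratios in the cases tried. This stands, and it limits what can be claimed.

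A reader might also infer that week one should become the primary rate, as the window that was sized. That does not follow either. Laboratory safety is checked on Fridays, so one scheduled draw falls in the seven days after a first bath, and any cumulative effect would drop out of the headline figure.

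The plan also has partial safeguards. Extra event-free days do not dilute the proportion of infants with any event. Hypothesis 1, a rate under 10%, reads most naturally as that proportion. Kaplan-Meier curves are to be considered for rash, and times of onset are logged. These soften the consequence. They do not repair the rate that the sample size section calls its primary goal, and the curves cover rash only.

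Finally, events may be too few for a split to say much. At the assumed ceiling of 5 per 1000, 243-280 week-one days yield only 1.2-1.4 expected events. That is true, and it is why the split should be descriptive.

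**Conclusion.** The mismatch is in the text and needs no outside fact. The rate is sized on 350 days at 7 per infant, follow-up runs to 12 weeks, and the analysis names no window. The sample size figures therefore do not give the precision of the reported rate. They also do not follow from 350 days: the correct values there are 70.6% and 29.5%, with a zero-event bound of 8.6 (one-sided) or 10.5 (two-sided) per 1000.

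The effect of pooling is conditional. If all events fell in week one, the pooled rate would be 0.47-0.78 of the early rate with fixed follow-up of 9-15 days, or 0.37-0.54 with exponential follow-up of the same means. With constant risk the two rates agree, and the only cost of a mismatched window is some precision. With accumulating risk the pooled rate exceeds the early one. All of this rests on unit mean stays standing in for time after the first bath, although those stays run from admission and participation can end sooner at catheter removal. The supported conclusion is that one pooled rate cannot show a change in risk over time, not that it will understate risk.

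**What to change.** In Data Analysis, keep the pooled rate as the primary rate. Report beside it the rate for days 0-7 after the first bath and the rate for later bathed days, each with an exact Poisson 95% interval, as descriptive results. Do not replace the primary rate with the week-one rate.

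In the Sample Size Justification, state which patient-days enter the primary rate, including whether days with baths on hold or in off-bath monitoring count. Then recompute the probabilities and the upper bound on that basis, saying whether the bound is one- or two-sided. If 350 days is kept, the figures are 70.6%, 29.5%, and 8.6 or 10.5 per 1000. Show expected patient-days only as a labelled assumption, for example 450-747 in total and 243-280 in week one if follow-up is exponential with the unit mean stays of 9-15 days.

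The cost is some wording, a short recalculation and two table rows. Baths and times of onset are already recorded, and treatment and enrolment do not change. The downside is that the period-specific intervals are wider than the pooled one.

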Full Body Skin Assessment. Study nurses will perform a full body skin assessment for skin irritation or open areas on infants prior to each bath. Following each bath, bedside nurses will conduct a full body assessment every 12 hours for the duration for the study (with the last assessment performed 36 hours after the last bath or prior to discharge- whichever occurs first). Full body assessment for altered skin integrity will be documented on the CHG Skin Assessment Log (Appendix D) provided for each participant. Full body assessment revealing untoward or adverse findings will also be recorded on the CHG Adverse Event Reporting Tool- Alteration in Skin Integrity (Appendix E) and reported to the PI.

CHG Measurement. Serum CHG levels will be quantified weekly by a clinical chemistry fellow with expertise using High Performance Liquid Chromatography coupled with tandem mass spectrometry (LC-MC/MS). Briefly, CHG will be extracted from 200uL of serum following deproteinization with 0.1% formic acid and addition of a deuterated CHG internal standard. Reversed phase HPLC separation and elution will be performed using a Waters Acquity® UPLC system with a C18 column. Detection and quantification will be achieved on a Waters Quattro™ triple-quadrupole mass spectrometer by electrospray ionization in positive ion mode (Chapman, et al 2013).

CHG blood levels. CHG blood level assays will be performed to determine CHG levels in study participants; but will not be used to inform clinical decision-making since safe blood levels of CHG are not known. Thus CHG blood level assays will not be used as the primary method of determining adverse reactions.

Instead, we will employ the current standard of care for determining adverse reactions to topically applied CHG, which is the visual and clinical assessment of nursing and medical staffs for symptoms of an adverse reaction. In this study, visual and clinical assessments for symptoms of an adverse reaction will serve as our primary measure for safety.

We plan to examine associations between CHG blood levels and other adverse reactions (skin irritation or open areas, abnormalities in liver and renal function tests) to help determine safe blood levels in infants 36 weeks PMA or older and less than 48 weeks PMA. Clinical decisions regarding potential reactions will be based on the evidence of adverse events from the visual and clinical assessments for symptoms of an adverse reaction.

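### The stated 83% and 40% chances of seeing an adverse event do not follow from 350 patient-days (about 71% and 30% do), and the 5.5 per 1000 mean upper bound is not reproduced at either assumed rate

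*Combined protocol and SAP*

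**What the plan says.** All the inputs stand in the second paragraph of Sample Size Justification in the combined protocol and SAP.

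- Exposure: "We propose following N=50 subjects over 7 days of post-exposure follow-up, for a total of 350 observation days".
- Ceiling for the rate: "we assume the rate of adverse events using CHG bath is lower than 5 events per 1000 days of post-exposure follow-up".
- Assumed rates: 3.5 or 1.0 events per 1000 days of follow-up.
- Chance of seeing an event at those rates: "the probability that at least one subject will experience an adverse event is roughly 83% or 40% respectively".
- Precision, from Monte Carlo simulation: "the mean upper bound for estimable rates is 5.5 events per 1000 days".

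The preceding paragraph names the rate per 100 patient-days as the main quantity to be estimated and promises an upper bound if no events occur. Data Analysis specifies the intervals only as follows: "Our inferential statistics will calculate 95% confidence intervals around these estimates".

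Other sections describe longer follow-up than 7 days. CHG Bath Intervention has baths continue "for up to 12 weeks post enrollment or until the CVC is removed or the patient is discharged". Under Full Body Skin Assessment, "bedside nurses will conduct a full body assessment every 12 hours for the duration for the study". Study Participation Ends also sets a 12-week maximum.

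**The concern.** The probability of at least one event is fixed once patient-days and rate are given, and the plan gives both. The printed percentages are too high for them. The upper bound also looks too low: 350 days with no events at all leaves an exact 95% limit well above 5.5 per 1000.

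The plan reports no other operating characteristics for N = 50, and Human Subjects classes the study as greater than minimal risk in infants whose safety profile is not known. Someone reading the plan would think the study more likely to reveal an event than its inputs allow. They would also think it could bound the rate close to the assumed ceiling of 5 per 1000, and so could read too much into a result with no events.

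**Working it through.** **1. Chance of at least one event, from the plan's inputs**

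Patient-days: 50 × 7 = 350. For a constant rate, P(at least one) = 1 − exp(−rate × days).

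- Rate 3.5 per 1000: expected events 0.0035 × 350 = 1.225; P = 1 − exp(−1.225) = 70.6%. Stated: 83%.
- Rate 1.0 per 1000: expected events 0.001 × 350 = 0.35; P = 1 − exp(−0.35) = 29.5%. Stated: 40%.

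The model does not matter. A binomial count by day gives 70.7% and 29.5%; a binomial count by infant gives 70.6% to 71.1% and 29.5% to 29.6%.

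**2. What would give 83% and 40%**

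- *More days, same rates.* −ln(0.17)/0.0035 = 506 days and −ln(0.60)/0.001 = 511 days. At 500 days the formula gives 82.6% and 39.3%.
- *Higher rates, same days.* −ln(0.17)/350 = 5.06 and −ln(0.60)/350 = 1.46 per 1000. Rates of 5.0 and 1.5 give 82.6% and 40.8%.
- *Percent of infants instead of rates.* 1 − 0.965^50 = 83.2% and 1 − 0.99^50 = 39.5%. This nearly coincides with the second reading, since 3.5% over 7 days is 0.035/7 = 5.0 per 1000 days (the ceiling in the same paragraph) and 1.0% is 0.01/7 = 1.43 per 1000 days.

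The documents do not decide between these.

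**3. Upper limit with zero events in 350 days (per 1000 days)**

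- Exact one-sided 95%: −ln(0.05)/350 = 8.6.
- Exact two-sided 95%: −ln(0.025)/350 = 10.5.
- Profile likelihood, two-sided 95%: 1.9207/350 = 5.49.
- Jeffreys, one-sided 95% (95% quantile of a gamma with shape 0.5, divided by 350): 5.49.

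The exact limit rises with the count, so no mean of exact limits at 350 days can be below 8.6. A zero-event exact limit of 5.5 would need −ln(0.05)/0.0055 = 545 days (one-sided) or −ln(0.025)/0.0055 = 671 days (two-sided).

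**4. Mean 95% upper limit at 350 days (per 1000 days)**

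Each entry is the sum, over Poisson counts, of the probability of the count times its upper limit. Simulation gave the same exact means.

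| Method | One-sided, true rate 1.0 / 3.5 | Two-sided, true rate 1.0 / 3.5 |
|---|---|---|
| Exact | 10.3 / 14.3 | 12.4 / 16.7 |
| Jeffreys | 7.4 / 11.8 | 9.3 / 14.0 |
| Profile likelihood | 6.1 / 10.9 | 7.9 / 13.0 |
| Wald | 2.5 / 7.7 | 2.8 / 8.6 |

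No entry is 5.5. The two-sided Wald mean reaches 5.5 only at a true rate of about 2.1 per 1000, which the plan does not assume.

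**5. Upper bound under the alternative readings**

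- 500 days, rates 1.0 / 3.5: exact means 7.7 / 11.7 (one-sided) and 9.2 / 13.4 (two-sided). The nearest value to 5.5 among the four methods is 5.7 (one-sided Jeffreys, rate 1.0).
- 350 days, rates 1.5 / 5.0: exact means 11.1 / 16.6 and 13.3 / 19.2. The nearest to 5.5 are 4.0 (two-sided Wald) and 7.1 (one-sided profile likelihood), both at rate 1.5.

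A reading that repairs the percentages therefore does not also repair the bound.

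**The case against.** - **The bound is undocumented, not shown to be wrong.** With the simulation inputs unstated, failure to reproduce 5.5 under guessed settings is weaker evidence than the percentages give. Averaging the two-sided Wald mean over the two assumed rates gives 5.66 at 350 days and 5.38 at 500. A one-sided Wald mean averaged over rates from 0 to 5 gives 5.59 at 350 days. Two methods give 5.49 with zero events, a case that the plan does mention. What stands is that this part is less firm. But none of the averaged readings gives 5.5 or is described in the plan, and a zero-event limit is a best case, whereas the plan reports a mean over simulations.
- **The percentages may be right and the exposure wrong.** Follow-up runs up to 12 weeks, and Setting reports average unit stays of 12.7 days (NICU) and 9 to 15 days (CICU, for infants under 2 months). Those are unit stays, not study follow-up, but an assumed mean of 10 days each would give 500 patient-days. This stands as a possibility. It changes which input must be corrected, and the paragraph still contradicts itself.
- **It is a pilot with a convenience sample.** No test drives N, and N, the Table 1 actions and the final observed intervals do not depend on these numbers. That is true, and it limits the consequence to what the study is said to be able to show.
- **The plan says 'roughly'.** That does not cover gaps of 10 to 12 points.

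**Conclusion.** The concern holds. Under the printed inputs, the chance of at least one event is 70.6% at 3.5 per 1000 and 29.5% at 1.0 per 1000. The stated 83% and 40% are too high by about 12 and 10 points. This rests only on a constant rate and 350 patient-days; variation in the rate between infants around the same mean could not raise the figures. Whether the days, the rates or the percentages are at fault cannot be settled from the documents.

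The 5.5 per 1000 bound is not reproduced at either assumed rate by the four usual methods, and with exact 95% limits it is impossible at 350 days whatever the true rate. A method not described in the plan might still produce it. With exact limits the study would bound the rate at 8.6 (one-sided) or 10.5 (two-sided) per 1000 at best, and on average at 10.3 to 16.7 over the two rates and both choices of sidedness. That is not close to the assumed ceiling of 5.

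**What to change.** Keep N = 50 and rewrite the second paragraph of Sample Size Justification.

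1. Reconcile patient-days, rates and percentages.
   - If 350 days and rates of 3.5 and 1.0 stand, state about 71% and 30%.
   - If longer follow-up is expected, state the expected total of patient-days and recompute all three figures.
   - If the rates were meant as percent of infants, or as about 5.0 and 1.5 per 1000 days, correct the rates.
2. Recompute the upper bound, naming the 95% interval method, its sidedness and the simulated true rate, and use the same method for the intervals in Data Analysis.
3. Report the zero-event limit separately from the mean. With exact limits at 350 days the zero-event limit is 8.6 (one-sided) or 10.5 (two-sided) per 1000. The means at true rates of 1.0 and 3.5 are 10.3 and 14.3 (one-sided) or 12.4 and 16.7 (two-sided).

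The cost is one paragraph and one short simulation, with no extra patients. If 350 days stands, the stated precision becomes less favourable.
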